Official title: Whitening Efficacy of Dentifrice Containing 10% High Cleaning Silica, 0.5% Sodium Phytate and 0.5% Sodium Pyrophosphate

NCT number: NCT04238429

Document date: 05/02/2018

Study Population and Design

This clinical trial was conducted at Guanghua School of Stomatology, Sun Yat-sen University, Guangzhou, China, from May to October 2018. The study protocols were approved by the institutional review board at Guanghua School of Stomatology, Sun Yat-sen University and were in good accordance with the World Medical Association Declaration of Helsinki on ethical aspects. This eight week study used a randomized, double-blind, parallel-group design.

The participants were informed of the study purposes and told that their participation was voluntary. Informed consent forms were signed. A total of 84 adults who met with the inclusion and exclusion criteria were invited to take part in the study. The inclusion criteria were: 1) aged 18 to 70 years old; 2) good general health; 3) able to attend the clinical examinations during the eight week study period; 4) possessing more than 20 natural permanent teeth that were uncrowned or not heavily filled with restorative materials, excluding third molars; 5) having a whole-mouth mean tooth composite stain index of more than 1.5 according to the Lobene Stain Index.⁽¹⁾ Exclusion criteria were: 1) severe oral diseases or chronic diseases; 2) advanced periodontal diseases; 3) pregnant or lactating females; 4) fluorosis or tetracycline teeth ; 5) wearing orthodontic bands or partial or removable dentures; 6) taking part in other clinical trials; 7) receiving prophylaxis during the previous 3 months or tooth whitening treatment during the past 6 months; 8) allergic to the study products.

Study procedures

Eligible patients were distributed into test and control groups randomly according to computer generated random numbers externally by a dentist. This dentist kept the randomization and group allocation information. All the other study personnel did not have access to the information during the course of the study.

The patients in the test group were given toothpaste containing 10% high cleaning silica, 0.5% sodium pyrophosphate and 0.5% phytic acid, while the patients in the control group were given a negative control toothpaste containing silica base without any active ingredient. All toothpastes were identical in appearance and taste. The

toothpaste was marked with its specific code number which represented its group allocation and this number was not decoded until the end of the study. The distribution of the toothpaste was made in a separate place to ensure that other study personnel and patients were unaware of group assignment.

The patients were asked to only use the assigned toothpaste and the same toothbrush to brush their teeth twice daily, in the morning and in the evening, for one minute. The patients were asked to maintain their other oral hygiene habits and daily eating habits. The patients were not allowed to use any other toothpastes and oral health care products, such as mouthrinse.

The patients came to the clinic to receive clinical examinations at baseline, 4 weeks and 8 weeks. The same examiner provided the clinical examinations during the course of the study. Firstly, evaluation of oral soft and hard tissues were performed. The examiner assessed soft and hard palate, oral mucosa, tongue, sublingual and mandibular areas, salivary glands and pharynx and larynx areas of each patient. Secondly, tooth stain of the anterior teeth were measured using the Lobene Stain Index. The index measures the area and intensity of extrinsic tooth stain on the facial and lingual surfaces of six lower anterior teeth and facial surfaces of six upper anterior teeth. The tooth surfaces were divided into two regions: body and gingival. For each part, the intensity and extent of extrinsic tooth stain were graded on a scale of 0-3. For stain intensity, the scale is scored as follows: 0= No stain; 1=Light stain (yellow to light brown or gray); 2=Moderate stain (medium brown); and 3=Heavy stain (dark brown to black). For stain area, the scale is scored as follows: 0= No stain detected; 1= stain covering up to 1/3 of the region; 2= Stain covering >1/3 to 2/3 of the region; and 3=Stain covering >2/3 of the region. Three variables on tooth stain were calculated for each patient. The mean Lobene stain area, intensity and composite scores were the sum of the scores on the recorded regions of tooth surfaces divided by the number of regions. The stain composite score for each region of the tooth surfaces was the stain area score multiplied by the stain intensity score.

At 4 weeks and 8 weeks, during the follow up examinations, the patients were also

questioned by an investigator about if they had experienced any adverse events. The adverse events included discomfort while brushing, bitter or alteration in taste, any allergic reactions arising from the use of the toothpastes and any feeling of changes on oral soft tissues. Any changes in general health conditions of the patients were also monitored.

After the patient finished each examination session, the acquired data were collected by the facilitator who kept the data. The other study personnel had no way to access the patient data during the course of the study.

Statistical analysis

According to the data from a previous study on tooth stain removal, the sample size of this study was calculated. Based on a standard deviation of 0.5 for tooth stain area score, a reduction in the mean stain intensity scores of 20% between the test and control groups, a power of 80%, a significance of 0.05, and an attrition of 10%, it was estimated that 40 patients needed to be included in each group.

Chi-square test and the independent t test were conducted to compare the differences between treatment groups on sex, age and baseline Lobene stain scores. ANCOVA with baseline Lobene score as the covariate was conducted to compare the differences between groups in follow-up Lobene area, intensity and composite stain scores. For each group, paired t tests were conducted to compare the differences between baseline and each of the two follow-ups in Lobene stain scores. All statistical analyses were two sided and at a significance level of $\alpha = 0.05$.

Study Protocol and Statistical Analysis Plan

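### Does a whole-mouth entry threshold let in patients with too little anterior stain to show an effect on an outcome scored on 12 anterior teeth?

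*Combined protocol and SAP*

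**What the plan says.** Two inclusion criteria under Study Population and Design matter here. Criterion 5 requires "having a whole-mouth mean tooth composite stain index of more than 1.5 according to the Lobene Stain Index". Criterion 4 requires "possessing more than 20 natural permanent teeth that were uncrowned or not heavily filled with restorative materials, excluding third molars".

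Study procedures then states that "tooth stain of the anterior teeth were measured using the Lobene Stain Index", and places the index on the "facial and lingual surfaces of six lower anterior teeth and facial surfaces of six upper anterior teeth". It adds: "The tooth surfaces were divided into two regions: body and gingival". Area and intensity are each graded 0 to 3 per region, and the composite is their product. Each patient's score is "the sum of the scores on the recorded regions of tooth surfaces divided by the number of regions".

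Under Statistical analysis, the follow-up area, intensity and composite scores are compared between groups by ANCOVA with the baseline Lobene score as covariate.

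**The concern.** The entry criterion speaks of the whole mouth and the outcome of the front teeth. If posterior stain counted at screening, a patient with heavily stained molars and nearly clean incisors could be enrolled. That patient would start close to zero on the outcome and have little room to improve, which would shrink the average difference between the groups and reduce power.

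Criterion 4 seems to add to this. It sets a tooth count for the whole dentition and does not ask that the 12 scored teeth be among those counted. One patient's mean could rest on 36 regions and another's on far fewer. The remedy looks cheap: tie the threshold to the anterior regions and set a minimum number of scorable anterior teeth.

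**Working it through.** **Regions in the index (Study procedures).** Six lower teeth × 2 surfaces + six upper teeth × 1 surface = 18 surfaces; 18 × 2 regions = 36. The composite per region runs from 0 to 3 × 3 = 9.

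**Criterion 5, index as defined.** A mean above 1.5 over 36 regions needs a sum above 1.5 × 36 = 54. Since 54/9 = 6, at least 7 regions must carry stain even at the maximum score. The anterior composite mean exceeds 1.5 by definition. The other two outcomes are also off the floor: each composite is at most 3 times the area score and at most 3 times the intensity score, so both of those means exceed 1.5/3 = 0.5.

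**Criterion 5, literal whole mouth.** The document gives no posterior scoring scheme, so one must be assumed. The posterior mean that just meets the threshold is:

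| Anterior composite mean | 28 teeth weighted equally: (1.5 × 28 − 12a)/16 | 112 regions (28 teeth × 2 surfaces × 2 regions), 36 anterior: (1.5 × 112 − 36a)/76 |
|---|---|---|
| a = 0.5 | (42 − 6)/16 = 2.25 | (168 − 18)/76 = 1.97 |
| a = 1.0 | (42 − 12)/16 = 1.88 | (168 − 36)/76 = 1.74 |

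These are modest scores on a 0 to 9 scale, so on this reading such patients could qualify.

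**What that could cost.** The plan states 40 per group, with SD 0.5, a 20% reduction, 80% power, two-sided 0.05 and 10% attrition. The control mean is not given, so 40 cannot be reproduced directly. Working backward, 40 × 0.9 = 36 evaluable per group, and the detectable difference is 0.5 × (1.960 + 0.842) × √(2/36) = 0.330, which implies a control mean of 0.330/0.20 = 1.65. Now let an assumed share f of patients have no anterior stain and no possible effect, so that the difference becomes (1 − f) × 0.330 with SD held at 0.5:

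| f | Power at 36 per group |
|---|---|
| 0 | 80% |
| 5% | 76% |
| 10% | 71% |
| 20% | 61% |
| 30% | 50% |

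Nothing in the document supports any value of f above zero. On the index reading f = 0.

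**Criterion 4.** More than 20 means at least 21. With 28 teeth (assumed full dentition without third molars), 28 − 21 = 7 may be unsound, leaving at least 12 − 7 = 5 scored teeth. That is 5 × 2 = 10 regions if all six lower teeth and one upper are lost, or 5 × 4 = 20 if all six upper and one lower are lost. Purely to show how extreme this is, suppose the seven unsound teeth fell at random among the 28. On average 7 × 12/28 = 3 would be anterior, leaving 9 of 12. The chance that all seven are anterior is C(12,7)/C(28,7) = 792/1,184,040, or about 0.07%.

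**The case for a change.** The strongest case for a change is that the document uses different words for the entry site and the outcome site and never says which regions feed the 1.5 threshold. On the literal reading the loss of power in the table is arithmetically possible. The gap in criterion 4 does not depend on how criterion 5 is read: there is no minimum number of scorable anterior teeth and no rule on whether crowned or heavily filled anterior teeth are recorded. The edit would need no new measurement.

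Part of this stands. The adjective fits poorly with an anterior-only index, and a minimum count would be reasonable practice. The consequences are much weaker:

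- The literal reading requires a screening procedure that appears nowhere in the document, against a definition that does appear.
- A patient with an anterior composite of 0.5 or 1.0 can still improve, so it is too strong to say that such patients cannot show an effect.
- Fewer recorded regions make a patient's mean more variable, but do not by themselves shrink the expected difference between groups.
- There is little ground for doubting that the stain can be removed: the index scores extrinsic stain, and fluorosis and tetracycline teeth are excluded.
- Exclusion criterion 5 removes wearers of partial or removable dentures, which narrows the group with several missing front teeth.

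**Conclusion.** No change to the plan is needed. Criterion 5 names the Lobene index, and Study procedures defines that index on 12 anterior teeth. The natural reading is that whole-mouth means the patient-level mean over all index sites in both arches. Entry and outcome then use the same 36 regions, and rewording the criterion would alter neither who is eligible nor any result.

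The missing minimum for anterior teeth is a gap that the scoring rule already handles sensibly, by dividing by the number of regions recorded. The limit of 5 of 12 teeth is a corner case, and no gain in power from a minimum can be shown from the document. Because patients are randomized and the comparison is adjusted for baseline, variation in anterior stain or in the number of regions would affect precision, not the validity of the comparison.

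This rests on the index as defined governing criterion 5. If posterior teeth were in fact scored at screening, some patients could have entered with low anterior stain. The trial would then have lost sensitivity, by an amount that depends on an unknown share of patients, but still without bias between groups.

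### Symptom adverse events are asked about only at weeks 4 and 8, with no baseline question and no described contact with patients who stop, so a few events per arm may be missed and prior brushing discomfort cannot be told from new

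*Combined protocol and SAP*

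**What the plan says.** All of this is in the combined protocol and SAP, under Study procedures unless stated.

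- **Visits.** "The patients came to the clinic to receive clinical examinations at baseline, 4 weeks and 8 weeks".
- **Tissue examination.** At these examinations, "Firstly, evaluation of oral soft and hard tissues were performed", by the same examiner throughout. This safety measure therefore has a baseline.
- **Symptom questions.** The timing is given as "At 4 weeks and 8 weeks, during the follow up examinations, the patients were also"; over the page, the same sentence says that they were "questioned by an investigator about if they had experienced any adverse events". Baseline is not mentioned.
- **Events listed.** "The adverse events included discomfort while brushing, bitter or alteration in taste", and then "any allergic reactions arising from the use of the toothpastes and any feeling of changes on oral soft tissues".
- **General health.** "Any changes in general health conditions of the patients were also monitored". No method or timing is given, and nothing is said about non-attenders.
- **Attrition.** Under Statistical analysis, the sample-size inputs include "a significance of 0.05, and an attrition of 10" per cent. No reason for leaving is given.

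The documents describe no reporting between visits, no question at withdrawal and no record of why a patient stopped. Statistical analysis contains no adverse-event analysis, so no denominator is set.

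**The concern.** Brushing discomfort, altered taste and allergic reaction can begin with first use and are plausible reasons to give up a toothpaste. Participants may use no other toothpaste, so one who cannot tolerate the assigned product has a reason to leave. A patient who leaves before week 4 is never asked about symptoms, and one who leaves between the visits is not asked again after week 4.

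There is a second gap at the start. Patients attend at baseline but are not asked about symptoms then, so a later report of brushing discomfort cannot be classed as new or long-standing.

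What is at stake is any statement about how well the toothpaste was tolerated. It would rest on those who came back, with no reference point for symptoms that some may have had already.

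**Working it through.** **1. Do the other safety measures fill the gap?**

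| Measure | Has a baseline? | Detects discomfort or taste? | Reaches patients who stop? |
|---|---|---|---|
| Questions at weeks 4 and 8 | No | Yes | None described |
| Oral tissue examination | Yes | No | No, clinic visits only |
| General-health monitoring | Not stated | Not stated | Not stated |

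No described measure provides both a baseline for symptoms and contact with leavers.

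**2. The plan's own figure.** Statistical analysis gives 40 per group including 10% attrition. This cannot be reproduced outright because no control mean is given. It is consistent with 36 evaluable patients per group, since 36 / (1 − 0.10) = 40. With SD 0.5, two-sided 5% and 80% power, 36 per group detects 0.5 × (1.960 + 0.842) × √(2/36) = 0.33. That is 20% of a control mean of about 1.65. The figure is not in dispute here; it supplies only the number of leavers.

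**3. Number who may not be asked.** 0.10 × 40 = 4 per arm, or 8 in total. With 84 patients split equally (the ratio is not stated), 0.10 × 42 = 4.2 per arm, or 8.4 in total. This is a ceiling for patients never asked, because anyone leaving after week 4 has answered once.

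**4. What could be missed.** The share of leavers with a complaint is not in the documents, so the whole range is shown. The assumptions are that all 4 leave before week 4 and that none of the other 36 has an event. The recorded result is then 0/36 in every row, with an exact two-sided 95% upper limit of 1 − 0.025^(1/36) = 9.7%.

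| Leavers with a complaint | Rate among all 40 | Exact 95% interval |
|---|---|---|
| 0 of 4 | 0/40 = 0% | – |
| 1 of 4 | 1/40 = 2.5% | – |
| 2 of 4 | 2/40 = 5% | 0.6% to 16.9% |
| 4 of 4 | 4/40 = 10% | 2.8% to 23.7% |

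The full-cohort rate passes 9.7% only in the last row, and by 0.3 percentage points. Even 4/40 against 0/40 gives a two-sided Fisher p of 0.12. The loss therefore affects the description of tolerability more than any formal test.

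**5. Effect of the missing baseline.** Let b be the proportion with existing brushing discomfort, the same in both arms in expectation because of randomisation. Let p be the true new-event rate in an arm. If existing complaints are all recorded as events and are independent of new ones, the recorded rate is b + (1 − b)p. The difference between arms is then (1 − b)(p_test − p_control). Absolute rates rise in both arms. The difference shrinks somewhat but keeps its sign.

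**The case against.** Several stronger conclusions are tempting, and the documents do not support them.

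- **That questioning is the only safety capture.** It is not. The tissue examination covers visible mucosal reactions at all three visits, and general health is monitored. The gap concerns symptoms, and patients who do not return.
- **That complaints drive the 10% attrition.** The 10% is a sample-size allowance with no cause attached. Missed events are possible, not shown, and a downward bias in one arm follows only if leaving is related to a reaction.
- **That existing complaints are counted as events.** Nothing says so. The altered-taste, allergy and felt-tissue items are worded as changes or as reactions to the product. The risk is mainly with brushing discomfort, and perhaps with bitter taste, where the wording is ambiguous. Severe oral disease, advanced periodontal disease and allergy to the products are exclusions, which limits the background further.
- **That early onset alone loses the event.** A patient with a week-1 complaint who attends at week 4 is asked about past experience and can report it.
- **That the true rate lies above a reported limit.** This needs the most extreme row in the working, and the plan does not propose to report a confidence limit.

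It can also be said that this is a short summary and that silence forbids nothing: spontaneous reports may have been accepted. That is fair. Even so, the text fixes when the questions are put, and following it as written leaves both gaps open. Randomisation and blinding deal with background complaints, but they do not correct a loss that happens after allocation and may differ by arm.

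**Conclusion.** The point holds as a limited one. Symptom questioning at weeks 4 and 8, without a baseline question or described contact with patients who stop, may miss symptom events in up to about 4 patients per arm. The most that this could hide is 10 percentage points of an arm's rate. That figure assumes 10% attrition, 40 per arm, every departure before week 4 and a complaint in every leaver; with half the leavers affected it is 5 points.

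Bias between arms depends on leaving being related to a reaction, which the documents neither state nor exclude. The baseline gap may inflate absolute rates, mainly for brushing discomfort, and is not expected to favour either arm. The two effects push recorded rates in opposite directions, so the net error in an absolute rate has no known sign.

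The stain scores and their analysis are unaffected. This is a minor improvement that costs very little.

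**What to change.** 1. Ask the same symptom questions at the baseline visit, and count as an event only a complaint that is new or worse than at baseline.
2. Have the investigator who already asks the questions put them once by telephone to any patient who stops or misses a visit, and record the reason for stopping.
3. Add to Statistical analysis a tabulation of adverse events by arm for all patients given toothpaste, stating how many in each arm were never asked.

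The cost is one added baseline item and about 8 short calls (10% of 84 is 8.4), made by existing staff. The recorded event count may change slightly: up through the calls, down through the baseline rule. Treatment, visits and the stain analysis stay as they are. If data collection has closed, the third item can still be applied to the report.

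### The sample-size sentence pairs the standard deviation of the stain area score with a reduction in the stain intensity score, so the stated 80% power is not established for either

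*Combined protocol and SAP*

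**What the plan says.** The sample size is justified in one sentence of the Statistical analysis section: "Based on a standard deviation of 0.5 for tooth stain area score, a reduction in the mean stain intensity scores of 20" per cent between test and control. With 80% power, significance 0.05 and 10% attrition, "it was estimated that 40 patients needed to be included in each group". The source is given only in general terms: "According to the data from a previous study on tooth stain removal, the sample size of this study was calculated". No figure or reference from that study is supplied. The same section makes all tests two-sided and compares the groups on area, intensity and composite scores by ANCOVA with the baseline score as covariate.

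Study procedures treats the scores as distinct: "Three variables on tooth stain were calculated for each patient". Intensity is graded by depth of colour and area by the fraction of the region covered. They share only the range of the scale: "For each part, the intensity and extent of extrinsic tooth stain were graded on a scale of 0-3". The composite for a region is the product of the two grades. The section also sets the schedule: "The patients came to the clinic to receive clinical examinations at baseline, 4 weeks and 8 weeks".

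The only stain level in the documents is an inclusion criterion in Study Population and Design: "having a whole-mouth mean tooth composite stain index of more than 1.5 according to the Lobene Stain Index".

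**The concern.** The sample size for comparing two means depends on the ratio of the difference to the SD, and both must describe the same variable. Here the SD is attached to area and the difference to intensity. A shared 0 to 3 range does not make the two SDs equal, because a patient's stain can vary in extent without varying in colour, and the reverse.

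What is at stake is how far the 80% can be relied on. This is the trial's only power statement, and a reader weighing a null result on area or on intensity would look to it. As printed, it supports neither reading. The group comparisons themselves do not depend on it.

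A secondary gap sits beside this. The 20% is relative, and no control mean is given to turn it into score points. Making the score names agree would therefore still leave 40 per group impossible to reproduce from the page.

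**Working it through.** **Inputs from the Statistical analysis section.** SD 0.5 (area); 20% relative reduction (intensity); power 80%; two-sided 0.05; attrition 10%; 40 per group. Not given: the control mean, the absolute difference, the visit, and whether 0.5 is the SD of a follow-up score or of a change.

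**1. Can 40 be reproduced?** Evaluable n per group = 2 × SD² × (1.960 + 0.842)² / difference², with difference = 0.20 × control mean. The control mean is missing, so the formula cannot be completed. This is a missing input; it is not a case of a full set of inputs giving some other number.

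**2. Working backwards, assuming that both inputs belong to one score.**
- Evaluable per group: 40 × 0.9 = 36.
- Normal approximation: 0.5 × √(2/36) × 2.8016 = 0.330 points; 0.330 / 0.20 = control mean 1.65.
- Unadjusted two-sample t test (noncentral t): 0.3348 points; 0.3348 / 0.20 = 1.674. With 35 evaluable per group it is 0.3397 points, or 1.698.

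So 40 per group corresponds to a difference of about 0.33 points and a control mean of roughly 1.65 to 1.70. The boundaries should not be read more finely, because they depend on the method and on the order of rounding, which the plan does not state. For example, a mean of 1.645 by the normal approximation gives n = 36.26, and 36.26 × 1.1 = 39.9, which also rounds up to 40.

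**3. How much the unprinted mean matters** (SD 0.5, noncentral t; both means are assumptions).

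| Assumed control mean | Difference | Evaluable per group | With 10% attrition |
|---|---|---|---|
| 1.5 | 0.30 | 45 | 45 / 0.9 = 50 |
| 2.0 | 0.40 | 26 | 26 / 0.9 = 28.9, so 29 |

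The normal approximation gives 49 and 28.

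**4. How much borrowing an SD from another score could matter.** Suppose the difference is 0.33 points (20% of an assumed 1.65) and the SD of that same score is not 0.5. Normal approximation, alternative SDs assumed:

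| SD of that score | Per group with attrition | Power with 36 evaluable |
|---|---|---|
| 0.4 | 27 | 94% |
| 0.5 | 42 | 80% |
| 0.6 | 58 | 65% |
| 0.7 | 79 | 52% |

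The row for 0.5 shows 42 because 36.04 rounds up to 37 before attrition is added. The error can run in either direction, and the documents do not say which row applies.

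**The case against.** The strongest reply is that this is a slip of one word. The planner's working is not in the documents, both scores run from 0 to 3, and a control mean near 1.67 is possible on that scale. A coherent calculation for a single score, with one label mistyped, fits the text. That stands as a possibility. A genuine mixing of two scores fits equally well, and nothing in the documents decides between them or says which word would be wrong. The defect is therefore in the calculation as written.

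A second reply is that the control mean, the visit and the reference may have been used and simply not printed. That also stands. They are reporting gaps and carry less weight than the mismatch.

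A third is that the planned analysis is baseline-adjusted ANCOVA, which would normally detect a somewhat smaller difference than the unadjusted figures above. This is right, and 0.33 points should not be taken as what the planned analysis delivers. But adjustment neither joins an area SD to an intensity effect nor supplies a mean.

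Finally, the document describes the trial in the past tense, so recruitment cannot change. The fix below does not ask for that.

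**Conclusion.** The sample-size sentence is wrong as written: 80% power with 40 per group is not established for the area score or for the intensity score. That conclusion rests on the wording alone. The figures of about 0.33 points and a control mean of 1.65 to 1.70 hold only if SD 0.5 and the 20% belong to one score, with 36 evaluable per group and no baseline adjustment.

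Three stronger readings are tempting, and the documents support none of them.
- *Forty is too few, or the trial is underpowered.* A control mean in the range above would justify about 40, a higher one would need fewer, and the mean is not stated.
- *The entry threshold of 1.5 is the control mean, so about 50 were needed.* That threshold applies to the composite, a product of area and intensity, and is a minimum at entry. It supplies neither mean.
- *The 20% means 0.20 points.* That would need 99 evaluable and 110 per group, and 36 evaluable would give about 40% power. But the text states a percentage reduction between groups, so this reading is not the natural one.

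The group comparisons are unaffected. What suffers is the credibility of the power claim.

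**What to change.** Identify the previous study and restate the calculation for one named score and one named visit. Take the SD, control mean and absolute difference all from that score in that study, and not from this trial's results. Say whether the SD is that of a follow-up score or of a change.

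If those inputs do not give 80% power with 40 per group, report the power that the fixed sample delivers, or the difference it detects at 80% power. Label the latter as a detectable difference and not as the planning target. Do not credit 80% power to any score for which it was not calculated.

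The cost is one paragraph and one reference, with no extra patients and no change of analysis. The downside is that the stated power may become less favourable.

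### Baseline-adjusted ANCOVA is the only between-group method and no missing-data rule is given, so on the natural reading the week-4 scores of patients without a week-8 score go unused at week 8

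*Combined protocol and SAP*

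**What the plan says.** The Study procedures section of the combined protocol and SAP sets three scoring visits: "The patients came to the clinic to receive clinical examinations at baseline, 4 weeks and 8 weeks".

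The Statistical analysis section gives one between-group method, a baseline-adjusted ANCOVA, used to "compare the differences between groups in follow-up Lobene area, intensity and composite stain scores". Within each group, "paired t tests were conducted to compare the differences between baseline and each of the two follow-ups in Lobene stain scores".

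The sample-size paragraph of the same section allows for loss to follow-up: "an attrition of 10%, it was estimated that 40 patients needed to be included in each group".

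The document does not define an analysis population. It states no rule for missing scores, no imputation or carry-forward, and no repeated-measures model. It does not name a primary visit or a primary score.

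**The concern.** An ANCOVA with baseline as its only covariate takes one outcome per patient. It cannot use the week-4 score of someone who has no week-8 score. With no missing-data rule, the natural reading is that such a patient leaves the week-8 comparison, although the trial already holds a baseline and a week-4 score for that patient.

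Two things are at stake. One is precision: the week-4 score carries information about the missing week-8 score. The other is bias. Patients can see their own stain, so someone who notices little change by week 4 is a plausible dropout. If that selection acts differently in the two arms, the week-8 difference among those who remain is shifted.

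**Working it through.** **1. The plan's own figure.** The target of 40 per group cannot be fully reproduced. The SD of 0.5 is given for the area score ("Based on a standard deviation of 0.5 for tooth stain area score"), the effect is given for another score ("a reduction in the mean stain intensity scores of 20% between the test and control groups"), and no control mean is stated. Working back:

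- Completers per group: 40 × 0.90 = 36.
- Difference detectable with 80% power, two-sided 0.05: 0.5 × 2.80 × √(2/36) = 0.33.
- Implied control mean: 0.33 / 0.20 = 1.65.

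Forward, a control mean of 1.65 gives 37 per group, or 42 after attrition, and 1.70 gives 34, or 38. These bracket 40, so 0.33 is used below as an assumed effect.

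**2. Precision.** Let n8 = 36 per group have a week-8 score, let n4 per group have a week-4 score, and let r be the week-4 to week-8 correlation given baseline. With random dropout, the week-8 variance under a likelihood-based repeated-measures model is proportional to (1 − r²)/n8 + r²/n4. ANCOVA of the observed week-8 scores gives 1/n8. The documents give no correlations, so r = 0.3 to 0.9 is assumed.

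If all four dropouts per group have a week-4 score (n4 = 40), the variance ratio is (1 − r²) + r² × 36/40 = 1 − 0.10r²:

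| r | Variance ratio | Effective n per group (36 / ratio) | Power at 0.33 |
|---|---|---|---|
| 0.3 | 0.991 | 36.3 | 80.4% |
| 0.5 | 0.975 | 36.9 | 81.0% |
| 0.7 | 0.951 | 37.9 | 81.9% |
| 0.9 | 0.919 | 39.2 | 83.2% |

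The reference is 80.0% with 36 per group; full data on 40 would give 84.0%. Power here treats 0.5 as the SD after baseline adjustment. If only half the dropouts have a week-4 score (n4 = 38), the variance falls by 0.5% to 4.3% and power is 80.2% to 81.7%. If none has one, there is no gain.

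**3. Bias.** Assumptions: total SD 0.5, baseline to follow-up correlation ρ = 0.5 to 0.7, week-4 to week-8 correlation 0.7 to 0.9, and about 10% of each arm lost after week 4.

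*One arm only.* Suppose the least improved 10% at week 4 leave one arm and dropout in the other is random. Removing the worst tenth of a normal distribution shifts the mean of the rest by 0.1755/0.9 = 0.195 SD. The approximate week-8 bias is 0.195 × s × r × c, where:

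- s = 0.5√(1 − ρ²) is the SD given baseline;
- r = (week-4 to week-8 correlation − ρ²)/(1 − ρ²);
- c = √((1 + ρ)/2) allows for selection on change rather than on the baseline-adjusted score.

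At the extremes:

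- ρ = 0.7, week-4 to week-8 correlation 0.7: 0.195 × 0.357 × 0.412 × 0.922 = 0.026.
- ρ = 0.5, week-4 to week-8 correlation 0.9: 0.195 × 0.433 × 0.867 × 0.866 = 0.063.

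So the bias is about 0.03–0.06, or 9% to 18% of 0.33. It is toward zero if the control arm loses its least improved patients, and away from zero if the test arm does. The result depends on the strength of selection and on what the SD of 0.5 describes. If 0.5 is the SD after baseline adjustment, milder selection in the control arm gives 0.02–0.04, and near-complete loss of its most stained patients gives 0.195 × 0.5 × r = 0.05 to 0.09 for r = 0.5 to 0.9.

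*One common rule.* Suppose the 8 least improved of 84 leave, whichever arm they are in, with an assumed week-4 effect of 0.15. Simulation gives a bias of about 0.02–0.03 toward zero, because a working toothpaste puts fewer test patients among the least improved.

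*Alike in both arms.* If each arm loses its own least improved patients to the same extent, the shifts cancel and the simulated bias is about zero.

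In simulations with 42 per group and 4 leaving each arm after week 4, the repeated-measures estimate was biased by at most about 0.005 in every case.

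**4. Scale.** With 38 per group left from 84, the week-8 standard error is s√(2/38): 0.357 × 0.229 = 0.08 to 0.433 × 0.229 = 0.10. The one-arm bias is therefore about a third (0.026/0.082) to just under two thirds (0.063/0.099) of one standard error.

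**The case against.** Four points on the other side carry weight.

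- **Missing-data handling is not stated.** A reader might infer that the plan prescribes a completers' analysis at each visit. It does not say so. The wording about each follow-up belongs to the within-group paired t tests, and imputation or carry-forward is neither stated nor excluded. This stands: what can be said is that the plan is silent, and that baseline-only ANCOVA naturally drops these patients.
- **Attrition is already budgeted.** The 40 per group includes it, and 84 were invited; losing about 8 leaves about 38 per group against the 36 implied. So a reader should not infer that the trial is underpowered on this account. Larger enrolment does not, however, remove bias from selective dropout.
- **Dropout related to response need not bias the comparison.** A reader might infer that ANCOVA of observed scores is unbiased only when dropout is unrelated to week-4 response. That is too strong, because like selection in both arms cancels. Blinding and matched toothpastes also make differential dropout less likely, though a common rule can still act unequally once the treatment works.
- **The benefit depends on timing.** The document does not say when the 10% would leave. Losses before week 4 gain nothing from the proposed model.

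Baseline-adjusted ANCOVA is also a standard and valid method, and with complete data the proposed model gives essentially the same week-8 estimate. These points limit the size of the concern. None of them gives a reason to leave collected week-4 scores unused.

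**Conclusion.** The concern holds in a limited form, as a cheap improvement. The only between-group method has no means of using a week-4 score when the week-8 score is missing, and the plan states no rule for that case despite expecting 10% attrition. The precision at stake is small and runs from nothing to the upper end of the table, according to how many dropouts have a week-4 score.

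Bias is conditional. It needs selection on week-4 response that differs in effect between arms, and in the main scenarios it stays below one standard error. All the bias figures rest on assumed correlations, an assumed difference of 0.33 and dropout after week 4. The documents give no dropout pattern, so they do not support a conclusion that the trial's result is biased, or biased in a particular direction.

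**What to change.** For each Lobene score (area, intensity, composite), fit one repeated-measures model to the week-4 and week-8 scores:

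- **Population:** all randomised patients with at least one follow-up score, analysed as randomised.
- **Terms:** group, visit, group × visit, the matching baseline score and baseline × visit.
- **Covariance and inference:** unstructured within-patient covariance, Kenward-Roger degrees of freedom.
- **Report:** the adjusted group difference and 95% CI at each visit.
- **Sensitivity analysis:** the per-visit ANCOVA on observed scores.

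State the missing-data assumption alongside. If another handling of missing week-8 scores was intended, the plan should say which.

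The cost is SAP wording and one standard model per score, with no new data, visits or patients. The downside is a slightly more complex model that relies on data being missing at random. Patients with no follow-up score are still excluded, so their number and group should be reported.
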